Project: MADCO-PC Study (Markers of Alzheimer's Disease and Cognitive Outcomes after Perioperative Care

Clinicaltrials.gov registration Number: NCT01993836

Date: July 15, 2016

Document: MADCO-PC Protocol Brief Summary 7-12-2016

MADCO-PC Protocol Summary

Purpose:

This study will examine the hypothesis that changes in the cognition (i.e. thinking and memory) after anesthesia and surgery are correlated with changes in markers of Alzheimers Disease in the fluid around the brain and spinal cord (i.e. cerebrospinal fluid, or CSF), and/or changes in brain connectivity. The investigators will also examine whether different types of anesthesia have different effects on these CSF markers of Alzheimers disease, or different effects on thinking and memory after anesthesia and surgery, or differential effects on the correlation between cognitive changes and CSF marker changes.

Outcome Measures:

Primary Outcome Measure: Assess the correlation between perioperative change in CSF Markers of Alzheimers Disease and perioperative cognitive change. [Time Frame: up to 6 weeks]

We will assess the magnitude of the Spearman correlation coefficient for the relationship between perioperative change in CSF Markers of Alzheimers Disease and the perioperative change in the continuous cognitive index score.

Secondary Outcome Measures:

1. Continuous cognitive index score change [Time Frame: 1 year]

We will examine the difference in the continuous cognitive index score over time in the subjects treated with propofol versus those treated with isoflurane, and versus such changes seen in non-surgical controls. We will also assess the correlation between perioperative change in CSF Markers of Alzheimers Disease and perioperative cognitive change in patients randomized to receive isoflurane vs propofol.

2. Assess CSF Markers of Alzheimers Disease [Time Frame: up to 6 weeks]

We will examine CSF Markers of Alzheimer's Disease over time in the subjects treated with propofol versus those treated with isoflurane, and versus any such changes seen in non-surgical controls.

3. Acute Perioperative CSF Tau/Abeta ratio change [Time Frame: 24 hours]

We will measure the perioperative change in the CSF tau/Abeta ratio from the start of anesthesia/surgery to 24 hours later, and compare this to changes seen in the non-surgical controls at the cognate time points.

4. Chronic Perioperative CSF Tau/Abeta ratio change [Time Frame: 1 year]

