We will measure the stability of any acute 24 hour postoperative changes in the CSF tau/Abeta ratio out to 6 weeks and 1 year later in surgical patients, and compare these changes to any changes seen over time in the non-surgical controls.

Enrollment Numbers, Inclusion and exclusion criteria

Targeted enrollment is 108 surgical patients who complete the 6 week follow up visit, which provides >80% power to detect a spearman correlation coefficient of 0.3 or greater (a low-

moderate correlation) for the aforementioned primary outcome measure. 54 non-surgical controls will also be enrolled as described below.

Ages Eligible for Study: 60 Years and older

Genders Eligible for Study: Both

Inclusion Criteria:

- Age 60 year or older
- Surgery scheduled to last at least 2 hours (including time for anesthesia induction, etc)
- English speaking ability.

Exclusion Criteria:

- Inmate of a correctional facility (i.e. prisoners).
- Pregnancy
- Documented or suspected family or personal history of malignant hyperthermia.
- Patient unable to receive either propofol or isoflurane due to allergy or other specific contraindication.

Inclusion criteria for the non-surgical controls are the same as those described above, with the exception of the second inclusion criteria (surgery scheduled to last at least 2 hours). Non-surgical controls (i.e. community dwelling older adults) will be recruited from several Duke research subject registries, and will be matched to surgical patients on a 2:1 basis (2 surgical patients for each non-surgical control) based on age, sex, and educational status. Non-surgical controls will undergo the same study procedures as surgical patients at the same cognate time intervals.

Study Procedures:

Cognition: Our full POCD cognitive test battery (as described in Newman MF et al, NEJM, 2001) is performed on study patients within one month (typically one week) prior to anesthesia and surgery, and then again six weeks and one year after anesthesia and surgery.

All patients are screened for delirium on postoperative days one through seven by our experienced neurocognitive testing team.

Biochemical Studies/Samples: CSF and peripheral blood samples are obtained immediately prior to anesthesia and surgery, 24 hours later, six weeks later, and one year later. These samples will be assayed for Alzheimer's disease biomarkers (including amyloid beta, tau and phospho-tau) as well as inflammatory markers and other biomarkers of interest.

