Cognitive Change from baseline to 6 weeks	As a numeric variable (continuous cognitive change) or as binary outcome (POCD w/>>1 or 2 SD drop)	Derive factor weights within sample and compare to that of historical non-cardiac population	Use bluecap database for cognitive data

3. Study population and datasets:

Inclusion Criteria: Patients undergoing urologic, general or other surgical procedures, aged 60 and above, English speaking **[Per PI will include all patients with BL and 6 week cognitive data available and run imputations to fill in missing CSF data in primary analysis]**

Exclusion Criteria: inmate of a correctional facility (i.e. prisoners), documented or suspected family or personal history of malignant hyperthermia, unable to receive either propofol and/or isoflurane due to allergy or other specific contraindication, receiving systemic chemotherapy after the first cognitive testing session and before the 6 wk or 1 year follow up cognitive testing sessions, major head trauma that occurs after the first cognitive testing session and before the 6 wk or 1 year follow up cognitive testing sessions.

Data Set Sources

Penn AD CSF data— Contains baseline, 24hr, and 6 week AD biomarker analysis (tau, abeta, p-tau)
Patient characteristics data—IT pull ticket 2494

Cognitive Data--Use BlueCap database and data entry from CRC groupAD Biomarkers (Primary Variable of Interest)

Variable names	Description	Specifications (e.g. formula)
CSF A beta	Measured BL, 24 hr, 6 weeks	Look at individual time points, trajectory, and change BL to 24 hr, and BL to 6 weeks
CSF tau		
CSF phospho-tau		
CSF tau/a beta		
CSF p-tau/a beta	Quotient of p-tau and a-beta at each time point	

4. Adjustment Variables

Candidate Covariates	Description
Anesthetic Type (randomized)	Propofol vs. Isoflurane group
Demographics	age, BMI, race, sex, years of education
Baseline Cognitive Status	MMSE score (raw and categorical [≥ 25 , 20-24, < 20]), mean cognitive index, domain scores
Clinical Factors	ASA status, surgical type (urology, orthopedics, plastics, thoracic surgery, general/abdominal, gynecologic etc), open incision vs laparoscopic approach, epidural block, regional block, vs no block, surgery duration (from incision to end surgery time stamps), IO BIS (mean of median filtered), ET aaMAC (mean of medians filtered), propofol dose, ketamine use, dexmedetomidine use, admitted to ICU by POD1

6. Statistical Methods and results

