 - b. Association of CSF change with binary cognitive outcome via t-tests or Wilcoxon rank sum tests.
 - i. Summary statistics on ACTIVATE _ResultsSummary_0727 sheet CSFchange
 - ii. Still need to determine how to run non-parametric test on MI datasets (as of 7/28)
 - c. Added 7/27/17: Association of baseline CSF with numeric baseline cognition and cognitive change via spearman correlation
- 3. Multivariate Analysis
 - a. Use linear and logistic regression to study association of CSF with cognition adjusting for patient characteristics
 - b. Candidate variables for model: age, ASA status, years of education, baseline cognitive index, baseline MMSE score, baseline CSF AD biomarker measures, CSF AD biomarker changes from before to after surgery (from before to 24 hrs postop, and from before to 6 weeks postop), DARS, mean of median end tidal MAC fraction (age adjusted), surgery type, surgery length, MAC-hours, cumulative propofol dosage
 - c. Adjustment variables added as indicated via univariate association with outcome and as allowed by sample size restrictions in model

- d. Model assumptions will be evaluated and performance measured
 - i. Numeric cognitive change: assess residual Q-Q plot, mse, R2
 - ii. Binary cognitive change: C-index, R2, GOF
- 4. Investigate CSF associations with individual cognitive domains in exploratory analysis (figure 3). This would help evaluate for the possibility that pre to post op changes in CSF AD biomarkers may be particularly related to changes in one particular cognitive domain (such as memory) rather than global cognition.

Hypothesis 2: AD biomarkers will increase from baseline to the 24 hours postop time point.

- 1. Data visualization of CSF change over time (BL, 24hrs, 6wk)—Figure 1
- 2. Calculate change from baseline to
 - a. 24 hrs—assess if change is significant via t-test or Wilcoxon Signed Rank Test
 - b. 6 week—assess if change is significant via t-test or Wilcoxon Signed Rank Test
- 3. CSF trajectory analysis (BL, 24hr, 6 week)—repeated measures mixed model

7. Proposed Tables and Figures

- 1. Table 1 describing baseline characteristics of the study cohort
 - a. Demographics: age, BMI, race, sex, years of education
 - b. Baseline Cognitive status: MMSE score (raw and categorical [≥ 25 , 20-24, < 20]), mean cognitive index, domain scores
 - c. Baseline CSF measures

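### C-index, R2 and mse for the Hypothesis 1 regression models are planned as apparent values after outcome-based screening, with no internal validation, so these secondary figures are optimistic

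*SAP*

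**What the plan says.** The regression plan is in SAP section 6, Hypothesis 1, item 3 (Multivariate Analysis).

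- Item 3b gives the pool, beginning "Candidate variables for model: age, ASA status, years of education, baseline cognitive index, baseline MMSE score, baseline CSF AD biomarker measures" and continuing through CSF changes, anesthetic exposure and surgical factors.
- Item 3c gives the selection rule: "Adjustment variables added as indicated via univariate association with outcome and as allowed by sample size restrictions in model". It states no p-value threshold and no maximum number of terms.
- Item 3d gives the performance measures: "Numeric cognitive change: assess residual Q-Q plot, mse, R2" and "Binary cognitive change: C-index, R2, GOF".

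The SAP states no sample size. Its population section says the analysis "will include all patients with BL and 6 week cognitive data available and run imputations to fill in missing CSF data in primary analysis". The only size to work from is in the protocol: "Targeted enrollment is 108 surgical patients who complete the 6 week follow up visit".

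Neither document mentions a hold-out set, resampling, shrinkage, adjusted R2 or an external cohort for these models. The historical sample (N=389) supplies cognitive factor weights only.

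**The concern.** Terms are kept because they happen to correlate with the outcome in this sample, and the fit is then measured against the same outcomes. Apparent C-index and R2 are therefore biased upward and mse downward, even if the true relationship is nil. A reader who sees a C-index near 0.70 could take it as evidence that CSF markers and clinical factors discriminate patients with POCD, when a value of that size can come from selection alone. Nothing in the plan would let the reader tell these two explanations apart.

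**Working it through.** **Inputs**

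| Input | Value | Source |
|---|---|---|
| Patients | 108 | Protocol, enrollment section |
| Non-CSF candidates | 11 variables, about 15 terms | SAP 3b |
| CSF candidates | 5 markers x (baseline, 24 h change, 6-week change) = 15 | SAP section 3 and 3b |
| Screening threshold | p<0.05, 0.10, 0.20 | Assumed; not stated |
| POCD rate | 30%, about 32 events (0.30 x 108 = 32.4); 20-40% also tried | Assumed; not stated |
| Cap on terms | none, or 10 events per term (3 terms at 32 events) | Assumed; 3c gives no number |

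The 11 non-CSF variables are age, ASA, education, cognitive index, MMSE, DARS, end-tidal MAC, surgery type, surgery length, MAC-hours and propofol dose. With ASA as one term and six named surgery types (five indicators), that is 10 + 5 = 15 terms. The full list is 15 + 15 = 30.

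**Step 1: the plan's own figure.** The protocol says 108 patients "which provides >80% power to detect a spearman correlation coefficient of 0.3 or greater". Power = Phi(atanh(0.3)/SE - 1.96), taking two-sided alpha 0.05, which is not stated. With SE = 1/sqrt(105) = 0.0976, 0.3095/0.0976 - 1.96 = 1.21, so power is 88.7%. With the 1.06/(n-3) variance for Spearman it is 86.9%. The claim is reproduced. It concerns the primary correlation; no sizing is given for the regression models.

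**Step 2: hand check of R2 under the null.** If k noise terms are fixed in advance, expected R2 is k/(n-1). A term kept by a screen at level alpha has mean squared z of 1 + 2 z phi(z)/alpha. At alpha = 0.05 this is 1 + 2 x 1.96 x 0.0584/0.05 = 5.58, or 5.58/107 = 0.052 of R2 per kept term.

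- All 30 screened: 30 x 0.05 = 1.5 kept, and 1.5 x 0.052 = 0.078. Fixed in advance, 1.5 terms would give 1.5/107 = 0.014.
- 15 screened, one CSF term forced in: 1/107 + 0.75 x 0.052 = 0.048. Fixed in advance, 1.75 terms would give 0.016.

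Most of the inflation comes from the screen, not from the number of terms in the final model.

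**Step 3: null simulation.** Predictors were pure noise, screened one at a time, then fitted by linear or logistic regression and scored on the same 108 patients (1,000 runs per setting, 30% events, no cap). R2 is for the linear model.

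| Screened | Threshold | Mean R2 | Mean C | P(C>=0.70) |
|---|---|---|---|---|
| 15 non-CSF, one CSF term forced in | 0.05 | 0.05 | 0.62 | 13% |
| | 0.10 | 0.06 | 0.65 | 23% |
| | 0.20 | 0.10 | 0.68 | 40% |
| All 30 | 0.05 | 0.07 | 0.64 | 27% |
| | 0.10 | 0.11 | 0.70 | 54% |
| | 0.20 | 0.16 | 0.75 | 82% |

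A repeat run with 32 events gave C of 0.61/0.65/0.68 and 0.65/0.70/0.75. The R2 values at p<0.05 agree with Step 2. On new patients the same fits had C of 0.50 and R2 of about -0.06 to -0.17. In relative terms, apparent squared error is 5-16% below the outcome variance, while error in new patients is 6-17% above it.

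**Step 4: sensitivity.**

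- Event rates of 20-40%, all 30 screened: C is 0.64-0.67, 0.69-0.72 and 0.73-0.78 at the three thresholds.
- Correlated CSF terms: C 0.63-0.73.
- Cap of 10 events per term: C 0.62-0.65 with P(C>=0.70) of 9-13% (15 screened), or C 0.63-0.70 with 24-46% (all 30).

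**Step 5: does the correction work?** Bootstrap optimism correction repeated the screen in each resample (all 30 terms, 30% events, 120 data sets x 60 resamples).

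| Threshold | C apparent | C corrected | R2 apparent | R2 corrected |
|---|---|---|---|---|
| 0.05 | 0.65 | 0.51 | 0.09 | -0.14 |
| 0.10 | 0.70 | 0.55 | 0.12 | -0.15 |
| 0.20 | 0.75 | 0.59 | 0.15 | -0.16 |

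The repeat run gave corrected C of 0.52/0.54/0.58, and 0.49/0.52/0.56 on the literal reading. Most of the optimism in C is removed, less completely at looser thresholds. R2 at p<0.05 is overcorrected somewhat (-0.14 against -0.08 on new patients). No imputation step was simulated.

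**The case against.** **Only adjustment variables are screened.** This stands as the literal reading. Item 3c names adjustment variables, item 3a makes CSF the exposure, and SAP section 4 lists no CSF marker among them. A reader might infer from 3b that about 30 terms are screened. The text does not establish that, so 30 is an upper case. Against this, section 4 offers covariates absent from 3b (among them BMI, race, sex, domain scores, block type and ketamine use), and the SAP does not reconcile the two lists, so 15 is not a firm ceiling either.

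**The plan limits terms by sample size.** This stands in part. It would be wrong to say that nothing restrains overfitting. But the limit has no number, and limiting how many terms are kept does not undo the effect of having chosen them on the outcome.

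**The inputs are assumed and the global null is extreme.** This stands as a limit on the size. Threshold, event rate and cap are all unstated. Baseline cognitive index enters the change score, so it is unlikely to be pure noise. The null runs isolate what chance contributes; they do not forecast the trial's result.

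**These are association models.** This stands, and it sets the weight of the point. No hypothesis, protocol outcome, proposed table or figure rests on C-index, R2 or mse. Item 3d nevertheless says performance will be measured, so the figures will exist and may be reported.

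**A bootstrap is prediction-model practice and leaves some optimism.** The second half is true (Step 5). Labelling values as apparent would be a lighter remedy, but it would not tell the reader how large the optimism is.

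**Conclusion.** The point holds as one about secondary performance measures: 3d scores the models on the patients whose outcomes chose the terms in 3c, with no correction planned. The literal-reading rows of Step 3 are the fairer guide to its size, with the rows for all 30 terms as the upper case. Both rest on 108 patients, 30% events, thresholds from 0.05 to 0.20 and predictors unrelated to cognition.

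Two stronger readings are tempting and are not supported. One is that the reported values will look good even if nothing predicts cognition. They can, but at p<0.05 on the literal reading C averages about 0.62 and reaches 0.70 in about one null data set in eight. With all 30 independent terms screened at that threshold, 0.95^30 = 21% of null data sets would keep no term at all. The other is that the main result is compromised. The primary outcome is a Spearman correlation between CSF change and cognitive change, which uses neither the screen nor these measures.

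**What to change.** In 3c, state the screening threshold, the maximum number of terms for each of the linear and logistic models, and whether CSF terms are screened or forced in. Say which candidate list governs, 3b or section 4.

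In 3d, report optimism-corrected C-index, R2 and mse beside the apparent values. Use a bootstrap (for example 500 resamples) that repeats the 3c screen in every resample. Run it within each imputed data set and average the results. Label every uncorrected value as apparent. Note that some optimism remains at looser thresholds: with no true predictor and all 30 terms screened, C was still about 0.55-0.59 after correction at p<0.10 and p<0.20.

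The cost is SAP wording and extra computing, with no new data. The downside is that the reported figures become less favourable, and corrected R2 may be negative.

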Project: MADCO-PC Study (Markers of Alzheimer's Disease and Cognitive Outcomes after Perioperative Care

Clinicaltrials.gov registration Number: NCT01993836

Date: September 5, 2017

Document: SAP_2405_Berger_v5

Statistical Analysis Plan

ACTIVATE: CSF trajectories

SAP Version: 5.0

SAP Date: 9/5/17

Author: [name]

Primary Investigator: [name]

Revisions/Notes:

V2.0 5/20/17: Revised SAP structure to highlight hypotheses of interest, added data flow diagram and table shell

V3.0 6/5/17: Made primary and secondary hypotheses to match order in ct.gov listing. Added in current table 1

V4.0 7/28/17: There are 2 patients whose CSF data has yet to be analyzed, currently analyzed with imputation but if results returned from the lab will want to incorporate that data into the analysis.

Study Objective: AD biomarker change in CSF and relationship with cognitive change.

Animal studies have shown that inhaled anesthetic agents increase the levels of Alzheimer's disease related neural markers (such as amyloid beta and tau). Several studies have measured blood serum markers indirectly related to Alzheimer's disease in patients randomized to inhaled versus intravenous anesthesia, no randomized controlled trial has ever examined these markers in the cerebrospinal fluid of patients given inhaled versus intravenous anesthesia. No randomized controlled study to date has ever examined whether inhaled anesthetics (versus intravenous anesthetics) alter brain levels of Alzheimer's associated markers in humans, and/or whether such changes (if they occur) correlate with POCD or other cognitive changes, or changes in brain structure or activity after surgery and anesthesia.

Here, we propose to measure Alzheimer's disease-related neural markers in the cerebrospinal fluid (CSF) of patients exposed to anesthesia during surgery, as well as in non-surgical controls (age matched community dwelling individuals age 60 and over). These studies should clarify the effect of common anesthetic agents on Alzheimer's disease related neural markers and cognitive outcomes.

1. Hypotheses:

- i. The degree of increase in AD marker CSF levels will be associated with cognitive outcomes.
- ii. AD biomarkers will increase from baseline to the 24 hours postop time point.

2. Outcomes:

Outcome	Description	Specifications	Variables and Source

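### The SAP pre-specifies no propofol-versus-isoflurane contrast for post-baseline CSF markers, 6-week cognitive change or their correlation, although protocol secondary outcomes 1 and 2 commit to all three

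*SAP*

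**What the plan says.** **Protocol, Secondary Outcome Measures.** Three comparisons of the randomised anesthetics are promised.

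- Item 1, cognition, with a 1-year horizon: "We will examine the difference in the continuous cognitive index score over time in the subjects treated with propofol versus those treated with isoflurane".
- Item 1, second part: the correlation between CSF change and "perioperative cognitive change in patients randomized to receive isoflurane vs propofol".
- Item 2, CSF markers (up to 6 weeks): to be examined "over time in the subjects treated with propofol versus those treated with isoflurane, and versus any such changes seen in non-surgical controls".

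**SAP, title and Study Objective.** The plan is headed "ACTIVATE: CSF trajectories". Its rationale is that "no randomized controlled trial has ever examined these markers in the cerebrospinal fluid of patients given inhaled versus intravenous anesthesia", and its closing aim is to clarify what common anesthetic agents do to the markers and to cognition.

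**SAP, analyses.** Neither hypothesis in section 1 compares the arms. Under Hypothesis 2 (section 6), item 2 tests change from baseline to 24 hours and to 6 weeks, and item 3 reads "CSF trajectory analysis (BL, 24hr, 6 week)—repeated measures mixed model". Anesthetic type appears in three places: among the candidate covariates in section 4, as the grouping for comparing patient characteristics in section 6, step 0, and in the list of imputation variables in the same step.

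**The concern.** A pooled before-after change shows whether a marker moved around surgery. It cannot attribute the movement to an agent, because every surgical patient had both surgery and an anesthetic. Randomisation is what permits that attribution, and no outcome analysis in this SAP is specified to use it.

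The nearest route to an arm estimate is the cognition regression under Hypothesis 1, item 3. The candidate list in 3b omits randomised group. Item 3c lets adjustment variables in by univariate screening and as sample size allows, so arm could enter from section 4. The same model may then hold CSF change, MAC-hours and cumulative propofol dosage. All are measured after randomisation, and the last two record exposure to the agents themselves. An arm coefficient beside them is not the total effect of assignment.

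An analyst who follows the SAP exactly could finish without an answer to the question that the SAP gives as its rationale. Arm contrasts produced later would be open to the objection that marker, time point and model were chosen with results in view. Section 6 already cites a results file.

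**Working it through.** **1. Commitments against specified analyses**

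| Protocol commitment, propofol vs isoflurane | What the SAP specifies |
|---|---|
| Cognitive index over time (outcome 1) | Association of 6-week change with CSF; arm may enter only by screening |
| CSF-cognition correlation by arm (outcome 1) | Pearson/Spearman coefficient with no split by arm and no arm-by-CSF term (Hypothesis 1, item 2a) |
| CSF markers to 6 weeks (outcome 2) | Change tests and mixed model by time point only (Hypothesis 2, items 2-3) |

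The proposed figures do not fill the gap. The one stratified CSF plot considered (section 7, Figure 1, f) is split by POCD. Step 0 compares characteristics by anesthetic type, and Table 1 includes baseline CSF and baseline cognition, so the gap concerns post-baseline outcomes only.

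**2. The protocol's own power figure**

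Inputs: "Targeted enrollment is 108 surgical patients who complete the 6 week follow up visit", and Spearman 0.3 with power above 80% (Protocol, Enrollment Numbers). A two-sided 5% level is assumed. Power = Φ(atanh(0.3)·√((n−3)/c) − 1.96), with n = 108 and atanh(0.3) = 0.3095.

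- c = 1 (Pearson): Φ(3.17 − 1.96) = 88.7%.
- c = 1.06 (Spearman): Φ(3.08 − 1.96) = 86.9%.

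The stated figure is reproduced. It concerns the pooled correlation, for which pooling is right.

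**3. What a pooled change says about the arms**

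With equal arms the pooled mean is the average of the two arm means. A pooled change of 0.25 SD is equally compatible with arm means of 0.5 and 0, 0.25 and 0.25, or 0 and 0.5. Those are arm differences of +0.5, 0 and −0.5 SD.

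**4. Precision of the missing contrasts**

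The documents do not state the allocation. I assume 54 vs 54 and show 72 vs 36 as a range, with a within-arm SD of 1.

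*Mean difference.* The standard error is √(1/54 + 1/54) = 0.192, or √(1/72 + 1/36) = 0.204.

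- Difference detectable with 80% power (noncentral t): 0.54 SD, or 0.58 SD at 72 vs 36. The normal approximation for equal arms, (1.96 + 0.84) × 0.192, gives 0.54.
- 95% CI half-width (t-based): 0.38 SD, or 0.40 SD at 72 vs 36.
- Power at 0.5 SD with equal arms: Φ(0.5/0.192 − 1.96) = Φ(2.60 − 1.96) = 74%.

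*Difference between two correlations, 54 per arm.* On the Fisher z scale SE = √(2c/51), which is 0.198 (c = 1) or 0.204 (c = 1.06).

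- 0 vs 0.3: Φ(0.3095/0.198 − 1.96) = 35%, and Φ(0.3095/0.204 − 1.96) = 33%.
- 80% power needs a z difference of 2.80 × SE = 0.555 to 0.571, that is, correlations of 0 vs 0.50-0.52.

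**5. Imputation**

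Arm is in the imputation list, but the list names no arm-by-CSF interaction. If a fraction m of CSF values is imputed with one slope for both arms, the difference in correlation shrinks to about (1 − m) of its size. At the SAP's expected maximum m = 0.10, 0.50 becomes 0.50 × 0.90 = 0.45. This assumes values missing at random and equal variances.

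**The case against.** The strongest reply is scope. The SAP is headed as a CSF trajectories plan. It also has no analysis of 1-year outcomes, control comparisons, MRI or delirium, all of which are in the protocol. That pattern fits a plan for part of the study, with the arm contrasts held elsewhere. This stands as a possibility. The SAP cites no such plan, however, and its own rationale is inhaled versus intravenous anesthesia. Its V3.0 revision note says that the hypotheses were ordered to match the registry listing. That note suggests an intention to follow the registered outcomes but does not establish full coverage.

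Three stronger readings are tempting, and the documents do not support them.

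- *The SAP guarantees that no arm contrast will be reported.* It is silent, and silence excludes nothing.
- *No arm effect on CSF is planned at all.* Section 4 lists anesthetic type as a candidate covariate without limiting it to the cognition models, and the mixed model's fixed effects are not spelled out. What can be said is that none is pre-specified in this document.
- *The pooled test hides an arm difference.* It addresses a different question and conceals nothing.

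It is also fair to say that these contrasts would be weakly powered. That is a reason to report them as estimates with intervals, not a reason to omit comparisons that the protocol promises.

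**Conclusion.** The point holds as a gap in pre-specification and should be fixed. All three arm comparisons in protocol secondary outcomes 1 and 2 lack a specified post-baseline analysis in this SAP, and nothing in it ensures that one is reported. Confidence is high on what the SAP does and does not specify. It is lower on the consequence, because a separate plan may exist.

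The primary pooled correlation is unaffected. The power figures in the working describe how precise the added contrasts would be. They do not measure harm, and they rest on an assumed allocation, a two-sided 5% level and 108 completers.

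**What to change.** Keep the pooled analyses. Either cite the plan that holds the arm contrasts, or add them here as secondary analyses by randomised group.

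1. **CSF.** Add arm-by-time to the planned mixed model. Baseline cannot be both response and covariate, so choose one form. Either keep baseline as a response with arm means constrained equal there, or use only 24 hours and 6 weeks as responses, with baseline as covariate and arm and arm-by-time as terms. Report isoflurane minus propofol with 95% CI at both times for each of the five measures. If one contrast is singled out, say that this is the team's choice. Protocol outcome 3 ("We will measure the perioperative change in the CSF tau/Abeta ratio from the start of anesthesia/surgery to 24 hours later") goes on to a comparison with non-surgical controls, so it does not supply a key arm contrast. The 6-week contrasts stay secondary, as in outcome 2.
2. **Cognition.** Report the arm difference in the 6-week cognitive index adjusted for its baseline, without CSF change, MAC, propofol dosage or other post-randomisation variables. State which plan covers the 1-year difference.
3. **Correlation.** Report Spearman coefficients by arm and their difference with 95% CI, combined across imputations on the Fisher z scale. Preferably let the imputation model allow the CSF-cognition relation to differ by arm.
4. **Status.** State that these contrasts are not separately powered, date the addition, and say whether results by arm had been seen.

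**Cost.** Arm, CSF and 6-week cognition are already in the merged or imputed data, and the sample size does not change. The extra work is modest but more than a few model terms: Spearman estimates must be pooled over imputations, and Hypothesis 1, item 2b, still leaves open how to run non-parametric tests on imputed data. Intervals will be wide, and a null contrast would not show equivalence. The evidence is weaker if the addition follows sight of results by arm.
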